### 3.3 Exploratory Objective Evaluation

- The pharmacokinetics of PRA023 in subjects with UC after multiple doses.
- The change from Baseline in serum and fecal inflammatory biomarkers (PD markers).
- The proportion of subjects in 3-component Modified Mayo Score response, 3-component Modified Mayo Score remission, endoscopic improvement, RHI

histologic remission, Geboes score histologic remission, and mucosal healing at Week 50.

- The change in Partial Mayo Score (with or without PGA component) over time.
- The change in Geboes Index and RHI from Baseline to Week 12 and Week 50.
- The exposure-response relationship of PRA023 on PD markers.

Within subpopulation of subjects on corticosteroid at study entry, the proportion of subjects in clinical remission and off of corticosteroid at Week 50.

- The long-term safety, tolerability, and efficacy of PRA023 through Week 168/170.

## 4 INVESTIGATIONAL PLAN

### 4.1 Study Design

This is a multi-center, double-blind, randomized, placebo-controlled proof of concept study designed to assess the safety, tolerability, and efficacy of PRA023 following 12 weeks of induction therapy in subjects with UC. This study will be conducted under the aegis of a DMC and will commence following the demonstration of an acceptable safety profile of PRA023 at a dose of  $\geq 500$  mg in multiple ascending dose study in normal healthy volunteers (Study PR200-101).

The study has 4 periods (Screening Period, Induction Period [IP], Open-Label Extension [OLE] Period, and Follow-Up [FU] Period). The study will have 2 Cohorts that will enroll subjects in a sequential fashion utilizing an adaptive design as described below.

**Cohort 1:** Following the Screening Period, approximately 120 eligible subjects with moderately to severely active UC will enter the IP and be randomized in a 1:1 fashion to receive IV administration of PRA023 1000 mg on Week 0/Day 1, followed by 500 mg on Weeks 2, 6, and 10, or placebo at the same timepoints. Randomization will be stratified by CDx status of positive (CDx+) or negative (CDx-) and prior biologic experience (yes/no) at Week 0/Day 1. Subjects who discontinue from the study drug will have a follow-up period of 12 weeks after last dose.

**Cohort 2:** Enrollment will continue into Cohort 2 when any stratification limit of Cohort 1 enrollment is completed. When approximately 80% of subjects in Cohort 1 (i.e., ~96 subjects) have reached Week 12 or early terminated from the study, the DMC will conduct an unblinded analysis of clinical efficacy in CDx+ subjects and will recommend whether to continue enrollment into Cohort 2. The sample size for CDx+ subjects (combining Cohort 1 and Cohort 2) will be approximately 40, in the case where Cohort 2 completes enrollment as planned. For Cohort 2, eligible subjects who are CDx+ will enter the IP and be randomized in a 1:1 fashion to receive IV administration of PRA023 1000 mg on Week 0/Day 1, followed by 500 mg on Weeks 2, 6, and 10, or placebo at the same timepoints. Randomization will be stratified by prior biologic experience (yes/no) at Baseline. Subjects who discontinue from the study drug will have a follow-up period of 12 weeks after last dose.

Subjects who complete the 12-week IP from either Cohort will have the option to enter OLE. During OLE, starting at Week 14 visit:

- Responders (defined as reduction from Baseline  $\geq 2$  points and  $\geq 30\%$  in 3-component Modified Mayo Score, accompanied by a reduction  $\geq 1$  in rectal bleeding subscore or absolute rectal bleeding subscore  $\leq 1$ ) will be re-randomized, stratified by CDx status of CDx+ or CDx-, to either 250 mg IV every 4 week (Q4W) or 100 mg IV Q4W, starting at Week 14 until Week 170
- Nonresponders will receive an open-label induction regimen of 1000 mg of PRA023 on Week 14, followed by 500 mg of PRA023 on Weeks 16, 20, and 24. Nonresponders who do not respond at Week 26 (per investigator discretion) should be discontinued from the study. Nonresponders who respond at Week 26 (per investigator discretion) will be re-

randomized to either 250 mg IV Q4W or 100 mg IV Q4W, starting at Week 28 until Week 168.

[figure not shown]
- For subjects assigned to the 100 mg Q4W OLE arm, the dose may be escalated to 250 mg Q4W if disease activity is not adequately controlled in the Investigator's opinion.

[figure not shown]
The study also includes an optional PK sub-study during the IP for subjects who consent to additional PK sampling.

#### 4.1.1 Study Schema

The overall schema for the study is noted below.

**Figure 1 Study Schema for Induction Period**

**Figure 2 Study Schema for Open-Label Extension Period**

Q4W = every 4 weeks; ® = Randomization

#### 4.1.2 Number of Subjects

Approximately 120 subjects with moderately to severely active UC will initially be randomized in Cohort 1. Enrollment will continue into Cohort 2 when any stratification limit of Cohort 1 enrollment is completed. Following interim analysis when approximately 80% of subjects in Cohort 1 (i.e., ~96 subjects) have reached Week 12 or early terminated from the study, the DMC will make a recommendation on the continuation of enrollment into Cohort 2. The planned sample size for CDx+ subjects (combining Cohort 1 and Cohort 2) will be approximately 40 in the case where Cohort 2 enrollment is completed as planned.

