--	--

	
For subjects assigned to the 100 mg Q4W OLE arm, the dose may be escalated to 250 mg Q4W if disease activity is not adequately controlled in the Investigator's opinion.
 
The study is being amended by the Sponsor to extend the OLE period beyond 132/134 weeks to Week 168/170 based on emerging safety data in both this study as well as a concurrent open-label Phase 2 study in Crohn's disease. This extension is to obtain safety data for at least 2 years' of PRA023 drug exposure for at least 100 subjects in this study, assuming 20% annual dropout rate. The OLE period may be further extended beyond 168/170 weeks based on emerging safety data in a future amendment.
 
The study also includes an optional PK sub-study during the IP for subjects who consent to additional PK sampling.

SAMPLE SIZE:	
The study is planned to randomize up to approximately 170 subjects, approximately 120 in Cohort 1 and up to 50 in Cohort 2. A sample size of 60 per arm in Cohort 1 will enable a statistical power of > 80% for the primary endpoint at 1-sided significance level of 0.025 using Cochran-Mantel-Haenszel (CMH), assuming clinical remission rate of 5% for placebo and 24% for PRA023. Additionally, the sample size will confer > 80% power to achieve statistical significance for the 1st secondary endpoint of endoscopic improvement with an overall 1-sided alpha level of 0.025, assuming the endoscopic improvement rates are 15% and 38% for placebo and PRA023 groups, respectively.
 
Additionally, for analyses of the CDx population (combining CDx+ subjects from Cohort 1 and Cohort 2), a sample size of 40 per arm will provide a statistical power of <math>\geq 80\%</math> at a 1-sided alpha level of 0.025, according to a group sequential design with a non-binding futility interim analysis when approximately 18 subjects per arm are anticipated to reach Week 12, assuming clinical remission rate of 5% for placebo and 31% for PRA023.

SUBJECT TYPE:	Male or female subjects $\geq 18$ years of age with moderately to severely active UC.
FORMULATIONS:	PRA023 will be supplied in 10 mL vials each containing 500 mg PRA023 (60 mg/mL concentrate for solution for infusion) for IV administration after reconstitution.

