	
endpoints in CDx+ subjects will be summarized and compared between PRA023 and placebo groups in FAS for CDx+, while the treatment difference will be estimated with 95% CI. Additional efficacy analysis will be detailed in SAP.
 
Interim Efficacy Analysis: An interim analysis will be carried out when approximately 80% of subjects (approximately 96 subjects) in Cohort 1 have reached Week 12 or early terminated from the study. The DMC will review the unblinded efficacy and safety data and recommend whether to continue enrollment into Cohort 2. Decision rules to continue Cohort 2 are to be determined according to the futility bounds of group sequential design of a sample size of 40 per arm with one interim analysis at the information fraction of 45%. Because the exact bounds will be calculated using the actual number of subjects with CDx+ included in the interim analysis, the final decision rules, along with sensitivity analysis, will be specified in the DMC SAP, prior to the interim analysis.
 
Adverse Events: AEs will be coded using the most current version of Medical Dictionary for Regulatory Activities (MedDRA®). A by-subject AE data listing, including verbatim term, preferred term (PT), system organ class (SOC), treatment, severity, seriousness criteria, relationship to drug, and action taken, will be provided. The number of subjects experiencing treatment-emergent adverse events (TEAEs) and number of TEAEs will be summarized by treatment using frequency counts for Safety analysis set. Medical History, chest x-ray, electrocardiogram (ECG), and physical examination will be listed by subject. Changes in ECGs and physical examinations will be described in the text of the final report.
 
Concomitant Medications: Concomitant medications will be coded using the most current World Health Organization (WHO) drug dictionary and listed by treatment.
 
Pharmacokinetics: Summary statistics of PRA023 concentrations and anti-drug antibody (ADA) by visit and by CDx+ and CDx-.

--	--

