### 8.1 Randomization

Subjects will be randomized in a 1:1 ratio based on two stratification factors: CDx status (+/-) and prior biologic experience (yes/no) in Cohort 1. If the study is expanded in Cohort 2, only CDx+ subjects will be randomized in a 1:1 ratio based on prior biologic experience (yes/no). Eligible subjects will be assigned a subject randomization number at baseline by the IRT system upon confirmation of study eligibility. Subjects who are re-randomized in OLE will retain their original subject numbers.

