### 8.2 Justification of Sample Size

The study is planned to randomize up to approximately 170 subjects, approximately 120 in Cohort 1 and up to 50 in Cohort 2. A sample size of 60 per arm in Cohort 1 will enable a statistical power of > 80% for the primary endpoint at 1-sided significance level of 0.025 using Cochran-Mantel-Haenszel (CMH), assuming clinical remission rate of 5% for placebo and 24% for PRA023. Additionally, the sample size will confer > 80% power to achieve statistical significance for the 1st secondary endpoint of endoscopic improvement with an overall 1-sided alpha level of 0.025, assuming the endoscopic improvement rates are 15% and 38% for placebo and PRA023 groups, respectively.

Additionally, for analyses of the CDx+ population (combining CDx+ subjects from Cohort 1 and Cohort 2), a sample size of 40 per arm will provide a statistical power of  $\geq 80\%$  at a 1-sided alpha level of 0.025, according to a group sequential design with a non-binding futility interim analysis when approximately 18 subjects are anticipated per arm reach Week 12, assuming clinical remission rate of 5% for placebo and 31% for PRA023.

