### 9.2 Interim Analysis

An interim analysis will be carried out when approximately 80% of subjects (approximately 96 subjects) in Cohort 1 have reached Week 12 or early terminated from the study. The DMC will review the unblinded efficacy and safety data and recommend on the continuation of enrollment into Cohort 2. Decision rules to continue Cohort 2 enrollment are to be determined according to the futility bounds of group sequential design of a sample size of 40 per arm with one interim analysis at the information fraction of 45%. Because the exact bounds will be calculated using the actual number of subjects with CDx+ included in the interim analysis, the final decision rules, along with sensitivity analysis, will be specified in the DMC SAP, prior to the interim analysis.

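### The combined CDx+ sample size is given as about 40 in three places and as 40 per arm (about 80) in four others

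*Protocol*

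**What the plan says.** Three places in the protocol give the size of the combined CDx+ population with no reference to treatment arms:

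- Section 4.1.2, Number of Subjects: "The planned sample size for CDx+ subjects (combining Cohort 1 and Cohort 2) will be approximately 40".
- Section 4.1, Study Design, Cohort 2 paragraph: "The sample size for CDx+ subjects (combining Cohort 1 and Cohort 2) will be approximately 40".
- The synopsis, Study Design, Cohort 2 paragraph, in the same words as 4.1.2.

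Four places use 40 per arm for the same population:

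- The synopsis sample-size text and section 8.2: "a sample size of 40 per arm will provide a statistical power of" at least 80%, at a 1-sided alpha of 0.025, for remission rates of 5% on placebo and 31% on PRA023.
- The synopsis interim text and section 9.2 base the decision to continue Cohort 2 on "futility bounds of group sequential design of a sample size of 40 per arm with one interim analysis at the information fraction of 45" percent.

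Three further statements bear on which figure is meant. The synopsis describes "a non-binding futility interim analysis when approximately 18 subjects per arm are anticipated to reach Week 12". Section 8.1 says that in Cohort 2 "only CDx+ subjects will be randomized in a 1:1 ratio based on prior biologic experience (yes/no"). Section 8.2 plans "approximately 120 in Cohort 1 and up to 50 in Cohort 2". Section 3.1 of the SAP addendum adds that, after its interim review, the DMC gave a total of 48 for Cohort 2.

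**The concern.** Read as written, section 4.1.2 describes a CDx+ population of about 40 subjects across both arms and both cohorts. The power statement needs twice that. Section 4.1.2 is where an ethics committee, an investigator or a regulator looks for the number of subjects, and the synopsis contradicts itself between its design and sample-size entries.

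The CDx+ comparison is not a side analysis. Clinical remission in CDx+ subjects is a secondary endpoint in the tested hierarchy, both in the protocol and in Table 1 of the SAP addendum. Anyone checking the final CDx+ count against 4.1.2 would see apparent over-enrolment of about twofold. Anyone computing power from 4.1.2 would conclude that the comparison was badly underpowered.

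**Working it through.** **Inputs.** Sections 8.1 and 8.2, with the matching synopsis text, give remission rates p0 = 0.05 and p1 = 0.31, 1-sided alpha 0.025, 1:1 allocation, 40 per arm, an interim at about 18 per arm, and a Cohort 2 of up to 50. Section 9.2 gives an information fraction of 45%. The SAP addendum gives alpha 0.0245 for the CDx+ endpoints (Table 1) and a Cohort 2 of 48 (section 3.1).

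**1. The stated power at 40 per arm.** The pooled-variance normal approximation for two proportions, with mean rate 0.18, is

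power = Φ{ [d − z·√(2·p̄·(1−p̄)/n)] / √[(p0(1−p0) + p1(1−p1))/n] }

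where d = 0.31 − 0.05 = 0.26 and z = 1.96. For n = 40:

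- null term: 1.96 × √(0.2952/40) = 0.1684
- standard error under the alternative: √(0.2614/40) = 0.0808
- power = Φ[(0.26 − 0.1684)/0.0808] = Φ(1.133) = 87%

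The claim of at least 80% is reproduced.

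**2. The same formula for a total of 40, that is 20 per arm.**

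- null term: 1.96 × √(0.2952/20) = 0.2381
- standard error: √(0.2614/20) = 0.1143
- power = Φ[(0.26 − 0.2381)/0.1143] = Φ(0.191) = 58%

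The choice of test does not alter the contrast. The exact rows enumerate the two binomials, with the CMH statistic taken in a single stratum:

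| Fixed design, 1-sided 0.025 | 40 per arm | 20 per arm |
|---|---|---|
| Normal approximation | 87% | 58% |
| Exact, CMH statistic | 91% | 62% |
| Fisher's exact test | 85% | 48% |

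At the addendum's alpha of 0.0245 the figures, in the same order, are 87%, 90% and 85% with 40 per arm, and 57%, 62% and 48% with 20 per arm.

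**3. Information fraction.** 18/40 = 0.45, as stated. With 20 per arm it would be 18/20 = 0.90.

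**4. Cohort sizes.** Every Cohort 2 subject is CDx+. A Cohort 2 of up to 50, or 48 in the addendum, exceeds a combined total of 40 before any CDx+ subject from Cohort 1 is counted. The interim alone expected 2 × 18 = 36 CDx+ subjects, and a total of 40 would leave room for four more.

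**5. Does the futility look upset the power claim at 40 per arm?** Section 9.2 leaves the bounds elsewhere: "the final decision rules, along with sensitivity analysis, will be specified in the DMC SAP, prior to the interim analysis". That document is not available, so the bounds below are assumptions. If the non-binding rule is followed at 45% information, power is P(Z1 ≥ c and Z2 ≥ 1.96). Here Z2 has mean 1.133 + 1.96 = 3.093, Z1 has mean 3.093 × √0.45 = 2.075, and their correlation is √0.45 = 0.671.

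| Assumed bound c (z scale) | Normal approximation | Exact two-stage, CMH statistic (18 then 22 per arm) |
|---|---|---|
| 0 | 86.7% | 89.7% |
| 0.5 | 84.9% | 88.4% |
| 0.8 | 82.3% | 86.7% |
| 1.0 | 79.5% | 84.5% |

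The normal approximation falls to 80% at about z = 0.97. The exact calculation stays above 80% at every bound tried. The power claim for 40 per arm is therefore credible with the look included.

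**The case against.** The best defence is that this is an omitted qualifier and nothing more. The sections that govern the statistics agree on 40 per arm, and no power, alpha, bound or analysis set is derived from the three unqualified sentences. The size of Cohort 2 was set elsewhere: a ceiling of 50 in the protocol, then 48 after the DMC's review. Power at 20 per arm describes a design that nobody planned, and the futility figures rest on assumed bounds. All of this is fair and limits the consequence. It does not remove the contradiction, because the section headed Number of Subjects still states half the planned size.

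A second objection is that the other figures exclude 40 without giving exactly 80. If the 36 CDx+ subjects expected at the interim all came from Cohort 1, then 36 + 48 = 84. Scaling them up to the full cohort gives 36/0.8 = 45, and 45 + 48 = 93. Conversely, 80 − 48 = 32, fewer than 36. Since Cohort 2 could open once any stratification limit in Cohort 1 was reached, some of its subjects may have counted at the interim, so this is not a second contradiction. About 80 is simply 40 per arm at 1:1, and 84 is within the tolerance of an approximate figure. What stands is that the sponsor should check any printed total against the 48.

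It is also true that 50 is a ceiling and that 48 came after the interim. The information fraction settles the matter without either.

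**Conclusion.** The inconsistency is real. The synopsis design text and sections 4.1 and 4.1.2 understate the planned CDx+ sample size by a factor of two, about 40 against about 80. The figure of 40 per arm is the one consistent with the 45% information fraction and the power claim, and a total of 40 cannot hold the planned Cohort 2.

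The power comparison assumes the protocol's remission rates and a fixed design. The conclusion is the same for the normal approximation, the exact CMH calculation and Fisher's test, and at either alpha level. The futility results depend on assumed bounds and do not bear on whether the texts agree.

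The consequence is confined to the stated figure. Sections 8.2 and 9.2 agree with each other, and nothing in the documents indicates that enrolment or the completed interim treated 40 as a total. It should be corrected, because a planned sample size is a figure the trial is held to.

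**What to change.** In the synopsis Cohort 2 paragraph, section 4.1 and section 4.1.2, replace the unqualified figure with approximately 40 per arm (about 80 in total). That matches the synopsis sample-size and interim text and sections 8.2 and 9.2. Before printing the total, the sponsor should confirm that it agrees with the Cohort 2 size of 48 in the SAP addendum.

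The cost is three wording edits at the next amendment. Enrolment, the interim analysis and the planned analyses are unaffected.

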#### 4.1.3 Subject Participation Duration

Time permitted from screening to dosing:	Up to 5 weeks
Duration of individual subject participation	
Induction:	12 weeks
Open-Label Extension:	Based on emerging safety data, until Week 168/170
Follow-Up:	12 weeks

## **4.1.4 Subject Numbering and Randomization**

### **4.1.4.1 Screening Numbers**

All subjects will be assigned a unique six-digit identification number. The first four digits will be the site number and the last two digits will be a number sequentially assigned by the site. This number will be used to identify the subject on all screening documents and during their study participation.

### **4.1.4.2 Randomization Numbers**

Subject enrollment and assignment of treatment will be managed through the use of a centralized Interactive Response Technology (IRT) system or another suitable system. Subjects who meet the required criteria for study participation will be assigned a subject randomization number which will be captured in the IRT. Subjects who are re-randomized in OLE will retain their original randomization numbers.

### **4.1.4.3 Blinding/Unblinding Procedures**

The Investigators and the Medical Monitor(s) will be able to unblind subjects through the IRT when it is medically imperative to know whether a subject is receiving PRA023 or placebo. In case of an emergency, the Investigator has the sole responsibility to assess and make the decision to unblind the subject's drug assignment if he/she feels this is warranted. Each Investigator will make arrangements to ensure that access to the secure internet site (i.e., individual user name and password) is maintained in strict confidence to prevent a compromise of subject blinding by non-study or unauthorized individuals.

Only in the event of an adverse event (AE) that the Investigator feels cannot be adequately treated without knowing the identity of the study drug should the medication code be broken for an individual subject. Every effort must be made to contact the Sponsor and/or the Medical Monitor as soon as possible thereafter if it is an emergency (no later than 24 hours after emergency unblinding). Similarly, if the Medical Monitor breaks the blind for the purpose of evaluating an emergent safety issue, the Medical Monitor will document within study correspondence the rationale, circumstances, and the person or persons being informed about the unblinding.

Access to randomization codes and corresponding treatment assignment will also be made available through the IRT to the appropriate Sponsor designee(s) and individual(s) who are responsible for reporting serious adverse events (SAEs) and suspected unexpected serious adverse reactions (SUSARs) to the regulatory authorities and should be accessed only in the event of a medical emergency. No other Sponsor personnel will have access to blinded subject treatment codes until all study data have been entered onto the study database and validated, and the database locked.

## 4.2 Study Subjects/Population

All subjects must meet the study inclusion and exclusion criteria outlined below in order to participate in the study. All subjects must also meet other site-specific criteria (e.g., screening and on-study criteria established by each site for COVID-19 mitigation) in order to participate in the study. These criteria will be amended by the site(s) as situation changes during the course of the study and should be documented by each site on site-specific COVID-19 risk mitigation plan. If absolutely necessary, for extenuating circumstances related to COVID-19, study activities may also be deviated as described by the study COVID-19 mitigation plan.

